## 7.2. Rationale and Discussion of Study Design

The available nonclinical and clinical data are sufficient to support a small, phase 2, proof-of-concept trial in adult participants with COVID-19. The initial dose-ranging part of the study will be used to select the safest dose that is likely to demonstrate clinical efficacy in Part 2 of the study and later trials. Safety reviews of data from Part 1 and interim data from Part 2 are designed to ensure participant safety prior to enrollment and treatment of a substantial number of participants.

The use of a placebo control will enable interpretation of safety and efficacy data. The study design requires that both treatment arms (varespladib and placebo) receive standard of care concurrently. Thus, participants will receive treatment in a timely manner while being evaluated for the potential clinical benefit of varespladib.

This study is designed to exclude as few potentially critically ill COVID-19 patients as possible. However, restricting the study population to severe patients and excluding the critical population will better enable interpretation of safety and toxicity data. In addition, excluding patients who already meet clinical criteria of chronic respiratory failure or who already require oxygen support will allow for clearer measurement of progression of acute respiratory failure and consistency with our underlying hypothesis.

Given the safety concern for cerebrovascular accidents (CVA) and myocardial infarction (MI) due to COVID-19, patients at risk of CVA and acute coronary syndrome (ACS) are excluded, and patients requiring any form of sedation, anxiolysis, or central nervous system (CNS) depressant within the 48 hours prior to enrollment that would interfere with neurologic assessments at enrollment are excluded. Given the known modest, transient increases in liver enzymes with varespladib, patients with liver abnormalities are excluded. Given the predominantly renal clearance of varespladib, patients with renal insufficiency are excluded.

The efficacy endpoints for this study were selected to demonstrate superiority of varespladib over placebo. The primary endpoint was selected to evaluate clear clinical benefit based on survival without respiratory failure, whereas secondary and exploratory endpoints were selected to evaluate a range of potential effects of varespladib over the course of treatment that may inform later trials.

## 7.3. Selection of Doses in the Study

The proposed dosing regimens of LY333013 (varespladib methyl) for the treatment of COVID-19 infection are based on the available PK/PD from previous clinical studies.

LY333013, which is administered orally, is the prodrug of LY315920, which is administered intravenously. LY333013 is rapidly absorbed and hydrolyzed to LY315920; therefore, only LY315920 is detected in the systemic circulation and LY333013 pharmacokinetics are based solely on concentrations of LY315920. Both formulations have been investigated in clinical studies in healthy participants and participants with various disease states.

The pharmacokinetics of LY315920 and LY333013 was investigated in 3 studies in participants with rheumatoid arthritis (Studies J4A-LC-EZZC, J4A-LC-EZZG, and H5P-MC-BWWC). Plasma clearance, steady-state volume of distribution, and drug elimination rates for LY315920 in participants with active rheumatoid arthritis are essentially similar to those observed in healthy participants.

The dose regimens in this study are supported by efficacy and safety data from clinical studies conducted by Eli Lilly in severe sepsis, including multiple organ failure. Two of the studies (J4A-LC-EZZE and J4A-LC-EZZF) support a specific dosing strategy in patients with severe sepsis. This strategy is based on a target plasma concentration of 800 ng/mL using the IV formulation of varespladib (LY315920), which was shown to be an effective concentration for inhibition of sPLA2. Studies in various indications indicated that this target concentration may be achieved with a dosing regimen of 500 to 1000 mg per day when given with food (Studies H5P-LC-BWWC, H5P-LC-BWXC, H5P-LC-BWWE, NCT00533039 [SPIDER-PCI], NCT00455546 [PLASMA 1], NCT00525954 [PLASMA 2], NCT01130246 [VISTA-16], and NCT00743925 [FRANCIS-ACS]).

The dose regimen for participants in Part 2 will be selected based on Part 1 of this study.

#### **7.4. Study Sites**

The study will take place at approximately 5 to 10 sites in the United States. Each site is anticipated to screen a sufficient number of participants to randomize approximately 5 to 15 participants. Sites will be selected to ensure access to a representative cross-section of the US population. A study site with a high recruitment rate may be allowed to recruit more participants if other sites have slow enrollment.

#### **7.5. End of Study Definition**

The clinical trial is considered completed when the last participant's final study visit has occurred.

## 8. PARTICIPANT POPULATION

### 8.1. Selection of Study Population

Investigators or their designees will maintain a screening log of all candidates who are considered for participation in this study, including reasons for ineligibility or refusal to participate. Consent, screening, randomization, and dosing may occur on the same day if test results are available. Participants who do not meet all of the eligibility criteria will not be enrolled. Approximately 90 participants will be randomized.

### 8.2. Study Entry Criteria

#### 8.2.1 Inclusion Criteria

A participant will be eligible for study participation if he or she meets all of the following criteria:

1. Participant is hospitalized with severe COVID-19 illness, defined in accordance with the FDA Guidance for Industry – COVID-19: Developing Drugs and Biological Products for Treatment or Prevention (May 2020):
  - a. Severe illness:
    - i. Symptoms suggestive of severe systemic illness with COVID-19, which could include any symptom of moderate illness or shortness of breath at rest, or respiratory distress
    - ii. Clinical signs indicative of severe systemic illness with COVID-19, such as respiratory rate  $\geq 30$  per minute, heart rate  $\geq 125$  per minute,  $\text{SpO}_2 \leq 93\%$  on room air at sea level or partial pressure of oxygen  $\text{PaO}_2/\text{fraction of inspired oxygen FiO}_2 < 300$
  2. Participant has a positive virologic nucleic acid amplification test (NAAT) indicating SARS-CoV-2 infection in a sample collected  $< 72$  hours prior to randomization.
  3. Participant is between the ages of 18 and 80 years at the time of enrollment.
  4. Participant (or legally authorized representative) provides informed consent prior to initiation of any study procedures.
  5. Participant agrees to not participate in another clinical trial for the treatment of COVID-19 or SARS-CoV-2 through Day 28.
  6. Participant has adequate hematologic status (in the absence of transfusion and growth factor support for at least 28 days), defined as follows:
    - a. Absolute neutrophil count (ANC)  $\geq 1.5 \times 10^9/\text{L}$
    - b. Platelet count  $\geq 75 \times 10^9/\text{L}$
    - c. Hemoglobin  $\geq 9 \text{ g/dL}$
  7. Participant has an Eastern Cooperative Oncology Group (ECOG) performance score of 0-2.

#### 8.2.2 Exclusion Criteria

A participant will be excluded from the study if he or she meets any of the following criteria:

1. Participant has mild, moderate, or critical COVID-19 defined in accordance with the FDA Guidance for Industry:

- a. Mild COVID-19:
  - i. Symptoms of mild illness with COVID-19 that could include fever, cough, sore throat, malaise, headache, muscle pain, gastrointestinal symptoms, without shortness of breath or dyspnea
  - ii. No clinical signs indicative of moderate, severe, or critical severity
- b. Moderate COVID-19:
  - i. Symptoms of moderate illness with COVID-19, which could include any symptom of mild illness (fever, cough, sore throat, malaise, headache, muscle pain, gastrointestinal symptoms) or shortness of breath with exertion
  - ii. Clinical signs suggestive of moderate illness with COVID-19, such as respiratory rate  $\geq 20$  breaths per minute, peripheral oxygen saturation ( $\text{SpO}_2$ )  $> 93\%$  on room air at sea level, heart rate  $\geq 90$  beats per minute
  - iii. No clinical signs indicative of severe or critical illness
- c. Critical COVID-19:
  - i. Respiratory failure defined based on resource utilization requiring at least one of the following:
    - Endotracheal intubation and mechanical ventilation
    - Oxygen delivered by high-flow nasal cannula ([HFNC] heated, humidified, oxygen delivered via reinforced nasal cannula at flow rates  $> 20$  L/min with fraction of delivered oxygen  $\geq 0.5$ )
    - Noninvasive positive pressure ventilation
    - ECMO, or
    - Clinical diagnosis of respiratory failure (i.e., clinical need for one of the preceding therapies, but preceding therapies not able to be administered in setting of resource limitation)
  - ii. Shock (defined by systolic blood pressure  $< 90$  mmHg, or diastolic blood pressure  $< 60$  mmHg or requiring vasopressors)
  - iii. Multi-organ dysfunction/failure

2. Participant has taken investigational medications within 7 days or 5 half-lives prior to enrollment, whichever is shorter.
3. Participant has required any new form of sedation, anxiolysis or central nervous system (CNS) depressant within the 48 hours prior to enrollment that would interfere with neurologic assessments at enrollment.
4. Has history of cerebrovascular accident or intracranial bleeding of any kind, acute coronary syndrome, myocardial infarction, or severe pulmonary hypertension.
5. Participant has chronic respiratory failure not associated with COVID-19, defined as prior need for home oxygen, need for home noninvasive positive-pressure ventilation (NIPPV) for reasons other than isolated sleep apnea, or other signs of chronic respiratory failure, in the investigator's judgment.
6. Upper gastrointestinal (GI) bleed evidenced by hematemesis, "coffee-ground" emesis or nasogastric aspirate, or hematochezia thought to originate from upper GI tract.

7. Participant has abnormal liver function defined as any 2 of the following at screening:
  - a. Total bilirubin  $\geq 2 \times$  ULN
  - b. Alanine aminotransferase (ALT)  $\geq 3 \times$  ULN
  - c. Aspartate aminotransferase (AST)  $\geq 3 \times$  ULN
  - d. Alkaline phosphatase (ALP)  $> 3 \times$  ULN
  - e. Gamma-glutamyl transferase (GGT)  $> 3 \times$  ULN
8. Participant has an estimated glomerular filtration rate (eGFR)  $< 60$  mL/min.
9. Participant has a known allergy or significant adverse reaction to varespladib-methyl or related compounds.
10. Participant is considered by the investigator to be unable to comply with protocol requirements due to geographic considerations, psychiatric disorders, or other compliance concerns; or has any serious medical condition or clinically significant laboratory, ECG, vital sign, or physical examination abnormality that would prevent study participation or place the participant at significant risk, as judged by the Investigator.
11. Participant is breast-feeding, pregnant, has a positive serum hCG pregnancy test, or is not willing to use a highly effective method of contraception for 14 days after treatment.  
Highly effective methods of contraception are as follows:
  - a. Combined (estrogen- and progestogen-containing) hormonal contraception associated with inhibition of ovulation (oral, intravaginal, or transdermal)
  - b. Progestogen-only hormonal contraception associated with inhibition of ovulation (oral, injectable, or implantable)
  - c. Intrauterine device, intrauterine hormone-releasing system
  - d. Bilateral tubal occlusion
  - e. Vasectomized partner
  - f. Sexual abstinence
  - g. Double-barrier method (condoms, sponge, diaphragm, with spermicidal jellies, or cream)

### **8.3. Participant Replacement**

Withdrawn participants will not be replaced.

Randomized participants withdrawn from the study may not reenter. The participant number for a withdrawn participant will not be reassigned to another participant.

## 9. TREATMENTS

### 9.1. Identification of Investigational Products

The investigational products (IPs) in this study are varespladib and matching placebo.

- Varespladib-methyl (LY333013)
  - 250 mg immediate-release oblong, white, film-coated tablet for oral administration
- Placebo
  - Oral formulation matched to the oral varespladib tablet

LY333013 contains the excipients anhydrous lactose United States pharmacopeia (USP)/National Formulary (NF), lactose monohydrate USP/NF, hydroxypropyl cellulose USP/NF, polysorbate 80 (vegetable source) USP/NF, microcrystalline cellulose USP/NF, croscarmellose sodium USP/NF, magnesium stearate (vegetable source) USP/NF, and the film coat Opadry II 85F18422 White.

### 9.2. Timing of Dose for Each Participant

In Part 1, varespladib or placebo will be administered in addition to institutional standard of care for 7 days at a dosage of 250 mg QD, BID, or TID (total doses of 250, 500, or 750 mg/day). The doses should be taken at the same times each day (+/- 2 hours for medication scheduling); ideally at least 5 hours apart. In Part 1, each participant will take 3 tablets per day with food. If IP is administered via nasogastric tube, it should be taken with food if possible.

Part 1 Randomized Treatment	Morning	Afternoon	Bedtime
250 mg QD	250 mg	placebo	placebo
250 mg BID	250 mg	placebo	250 mg
250 mg TID	250 mg	250 mg	250 mg
placebo	placebo	placebo	placebo

In Part 1, any dose that is missed should not be taken later that day. This includes Day 1; if a participant is enrolled in the afternoon or evening, only the afternoon and/or evening doses should be taken. If 7 complete days of dosing have not been completed by the end of Day 7, then the remaining doses will be administered on the appropriate schedule on Day 8. Examples:

- On Day 1, a participant who is enrolled in the morning should take the morning dose in the morning, the afternoon dose in the afternoon, and the bedtime dose at bedtime. No doses will be taken on Day 8.
- On Day 1, a participant who is enrolled in the afternoon should take the afternoon dose in the afternoon and the bedtime dose at bedtime. The last morning dose will be taken in the morning on Day 8, completing study treatment.
- On Day 1, a participant who is enrolled in the evening should take the bedtime dose at bedtime. The last morning and afternoon doses will be taken in the morning and afternoon, respectively, on Day 8, completing study treatment.

In Part 2, varespladib or placebo will be administered in addition to institutional standard of care for 7 days using the dose regimen selected from Part 1. For Part 2, the dose regimen for placebo will match the treatment regimen. The dose regimen selected for Part 2 will not include placebo doses used to maintain the blinding in Part 1. For example, if BID dosing is selected for Part 2, then the afternoon dose will be eliminated, and only morning and evening doses will be given for 7 days. If QD dosing is selected for Part 2, then only one dose will be administered per day for 7 days.

The doses should be taken at the same times each day (+/- 2 hours for medication scheduling), with food. As in Part 1, if IP is administered via nasogastric tube, it should be taken with food if possible. For Part 2, missed doses should be taken as soon as possible. Doses should be spaced evenly, but if a dose is missed, an interval of at least 5 hours between doses is recommended. If 7 complete days of dosing have not been completed by the end of Day 7 for Part 2 patients, then the remaining doses will be administered on the appropriate schedule on Day 8.

### **9.3. Dose Adjustment Criteria**

Dose adjustment is not allowed in this study.

### **9.4. Premature Participant Withdrawal**

All participants will be advised that they are free to withdraw consent from participation in this study at any time, for any reason, and without prejudice. The investigator should make every reasonable attempt to keep participants in the study, even if IP is discontinued; however, participants must be withdrawn from the study if they withdraw consent to participate. Participants should be listed as having withdrawn consent only when they no longer wish to participate in the study and no longer authorize the investigators to make efforts to continue to obtain their outcome data. Investigators must attempt to contact participants who fail to attend scheduled visits by telephone or other means to exclude the possibility of an AE being the cause of withdrawal. Should this be the cause, the AE must be documented, reported, and followed as described in [Section 11.2](#).

If a participant withdraws consent before completing the study, the reason for withdrawal of consent and the date of discontinuation will be recorded on the appropriate page of the electronic case report form (eCRF). Whenever possible and reasonable, the evaluations that were to be conducted at the completion of the study (see [Section 10.2.3.5](#)) should be performed at the time of premature discontinuation from the study, regardless of whether the participant has received study drug or not.

### **9.5. Discontinuation of Study Intervention**

#### **9.5.1 Individual Participant Halting Criteria**

If a clinically significant finding is identified (including, but not limited to, deterioration from baseline) after enrollment, the investigator or qualified designee will determine if any change in participant management is needed. Every effort should be made to administer the planned doses. Dosing should be held for a participant who experiences any of the following toxicities:

- Any Grade  $\geq 2$  creatinine increase ( $> 1.5 \times$  baseline or ULN)
- Any new, treatment-emergent occurrence of any of the following adverse events of special interest:

- Cerebrovascular accident
- Acute coronary syndrome
- Supraventricular arrhythmia requiring urgent medical intervention
- Any ventricular tachycardia/fibrillation including Torsade de Pointes
- Hepatic toxicity with AST and/or ALT  $\geq 3 \times$  ULN for 2 days or  $> 5 \times$  ULN on one occasion

If a participant becomes unable to swallow the IP due to worsening of their condition, nasogastric administration or a dose delay may be considered in consultation with the medical monitor. In general, treatment with IP should continue for the full 7 days unless the participant is unable to continue treatment or if it is the participant's best interest to discontinue treatment. If a participant must discontinue IP, every effort will be made to continue the participant in the study through Day 60. If a participant experiences an SAE judged to be related to the IP, the treatment for that participant will be permanently discontinued from the IP, but every effort will be made to continue the participant in the study through Day 60.

Any new clinically relevant adverse finding will be reported as an adverse event (AE) as defined in [Section 11.1](#).

Discontinuation from IP does not mean discontinuation from the study, and remaining study procedures should be completed as indicated by the study protocol.

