### **9.5.2 Management of Acute Kidney or Liver Injury**

Acute kidney/liver injury has been reported as a possible complication during the disease progression of COVID-19.

Extra caution and monitoring will be exercised when treating patients with COVID-19-induced hepatic dysfunction. Given the relatively short duration of treatment (7 days) compared to previous studies with varespladib and the transient nature of hepatic enzyme elevation, subjects with acute liver injury will continue IP and be closely monitored with clinic visits and repeated blood work including liver function tests on Days 14 and 28. If hepatic enzymes exceed the hepatic toxicity limits specified in [Section 9.5.1](#), IP should be discontinued. However, every effort will be made to continue the participant in the study through Day 60.

In the event of acute kidney injury secondary to COVID-19, the subsequent dose of the study drug will be withheld and will be recommenced once renal parameters become normal and an interval of at least 5 hours is available before the next dose. Once recommenced, IP will be given through the original 7-day treatment period and the missed dose will not be taken. If renal function is persistently abnormal and the participant misses study drug more than 24 hours, their IP treatment should be discontinued.

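### Protocol 9.5.1 holds dosing and Protocol 9.5.2 discontinues IP at the same hepatic limits

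*Protocol*

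**What the plan says.** Protocol Section 9.5.1 gives a list of toxicities under the instruction "Dosing should be held for a participant who experiences any of the following toxicities". The list contains a creatinine criterion and several events of special interest. Its hepatic item begins "Hepatic toxicity with AST and/or ALT" and sets two alternative limits: at least 3 × ULN for 2 days, or above 5 × ULN on one occasion.

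Section 9.5.2 deals with acute kidney and liver injury. For the liver it says two things in turn:

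- The general rule is that "subjects with acute liver injury will continue IP". Close monitoring is asked for, and the only days the sentence names for liver tests are Days 14 and 28.
- The section then points back to the limits of Section 9.5.1. Where enzymes go beyond them, the instruction is "IP should be discontinued", with follow-up to Day 60 still sought.

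For the kidney, the same section describes a dose that is withheld, a condition for restarting, and a point at which treatment is discontinued.

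Section 11.2.2.3 defines two separate actions taken for an AE: IP interrupted, which is temporary, and IP withdrawn, which is termination. SAP Section 2.2.2 lists AEs leading to discontinuation of IP among the safety endpoints. SAP Section 9.1.1 plans a table and a listing of TEAEs leading to withdrawal of study drug.

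**The concern.** A site with a participant at the hepatic limits finds two instructions. Under 9.5.1 dosing is held, and nothing says whether or when it may resume. Under 9.5.2 treatment ends. Two sites could follow the protocol in good faith and act differently on the same laboratory value.

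The matter touches both participant safety and a reported count. The protocol names modest, transient liver enzyme increases as a known effect of the drug (Sections 5.3 and 7.2), so this rule is relevant here. An event recorded as an interruption stays out of the discontinuation table, while the same event recorded as a withdrawal enters it. The SAP specifies no matching table for interruptions, so the difference would not show up elsewhere in the summaries. In Part 1 the arms are very small, and the DSMB recommends the Part 2 dose from the Part 1 safety results (Protocol Section 12).

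**Working it through.** The plan gives no figure on this point to reproduce. The check sets the texts side by side and adds some day and proportion arithmetic.

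**1. Same trigger, two actions**

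| | Section 9.5.1 | Section 9.5.2 (liver) |
|---|---|---|
| Trigger | AST and/or ALT ≥ 3 × ULN for 2 days, or > 5 × ULN once | The 9.5.1 limits, by cross-reference |
| Wording at the boundary | Experiencing the toxicity, so a value equal to 3 × ULN counts | Exceeding the limits, so read literally a value equal to 3 × ULN does not count |
| Action | Dosing held | IP discontinued |
| Restart rule for the liver | None | None |
| Stated to be final | No | Yes, by the word discontinued |

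**2. Does the protocol treat a hold and a discontinuation as different?** Three places indicate that it does.

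- Section 11.2.2.3 has one category for a temporary stop and another for termination.
- The kidney rule in 9.5.2 shows a withheld dose that is later resumed, with discontinuation as a further step.
- Section 9.5.1 itself speaks of permanent discontinuation, but only for an SAE judged related to the IP.

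**3. Size of one reclassified participant** = 1 / (participants in the arm).

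- Part 1 active arm (5 of the 18 in the 5:5:5:3 allocation): 1/5 = 20 percentage points.
- Part 1 placebo arm: 1/3 = 33 points.
- Part 2 arm as planned (72 at 1:1, so 36): 1/36 = 2.8 points.

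**4. Timing of liver tests against dosing.** The last dose is on Day 7, or on calendar Day 8 at the latest (Schedule of Events, note i). The Day 14 and Day 28 visits each have a window of ± 2 days.

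- Earliest Day 14 visit: 14 − 2 = Day 12. That is 12 − 8 = 4 or 12 − 7 = 5 days after the last dose.
- Earliest Day 28 visit: 28 − 2 = Day 26. That is 26 − 8 = 18 or 26 − 7 = 19 days after the last dose.
- Blood chemistry, which includes ALT and AST (Section 10.3.3.1.1), is scheduled during dosing on Days 4 and 7 (Sections 10.2.2.4 and 10.2.2.7), 7 − 4 = 3 days apart.

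The two days named in 9.5.2 therefore cannot fall within dosing. Scheduled on-treatment liver tests do exist, but 9.5.2 does not mention them, and neither section says how the 2-day limit is to be assessed.

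**The case against.** The best defence is that the sections are meant to be read in sequence. Section 9.5.1 is a generic list under a parent heading about discontinuing the intervention, so the hold would be the immediate step and 9.5.2 the organ-specific outcome. The kidney text has that shape, and no passage allows a restart after a hepatic hold. This is plausible, and it may be what was intended. It is stated nowhere, however. Section 9.5.1 also asks that every effort be made to give the planned doses and that treatment generally run its full 7 days, which could lead a site to see the hold as temporary.

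A second defence is that the effect on the analysis is not shown. That stands in part. The documents do not say how many participants would reach the limits, and the effect on the discontinuation count needs an event at the limits that sites handle or record differently.

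A reader might also infer more than the documents support:

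- *That continuing IP in acute liver injury contradicts stopping it.* The sentence that follows in 9.5.2 stops IP once the limits are exceeded, so the continue text is naturally read as applying below them.
- *That liver enzymes are not tested during dosing, or that Days 14 and 28 conflict with the dosing period.* Chemistry is scheduled on Days 4 and 7. The later days add follow-up and contradict no other passage.
- *That the 2-day limit cannot be met.* The text does not require consecutive days, inpatients are assessed daily under standard of care and extra tests are not barred. The alternative limit needs only one result.

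**Conclusion.** The point holds for the hold/discontinue difference. Sections 9.5.1 and 9.5.2 attach different actions to one set of hepatic limits, and their threshold wording differs at the ≥ boundary. The conclusion rests on reading the two words as the protocol's own action categories define them, and on the absence of any text that puts the two steps in order.

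The consequence is limited to participants who reach the limits. For each of them, the handling and the classification in the discontinuation table are open. In a Part 1 active arm one such participant accounts for 20 percentage points. SAP Section 10 leaves the safety analysis for Part 1 unchanged, so that count will be reported. The efficacy analysis rules do not depend on this point.

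The naming of Days 14 and 28, and the undefined way of assessing the 2-day limit, are matters for clarification and not contradictions.

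**What to change.** The sponsor and medical monitor should reconcile Sections 9.5.1 and 9.5.2 so that one action and one threshold wording apply to the stated hepatic limits. If a sequence of steps is intended, the text should say so. Which clinical rule applies is theirs to decide, and this review takes no position on it. The reconciled wording should map onto the action categories in Section 11.2.2.3, so that the count of AEs leading to discontinuation has one meaning.

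As a secondary clarification, the monitoring sentence in 9.5.2 should be aligned with the on-treatment chemistry on Days 4 and 7 and with how the 2-day limit is to be assessed during dosing.

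Part 1 enrolment is complete, so new wording cannot change how those participants were handled. For them, the report can list any hepatic event at the limits with the action recorded, which the CRF already collects (Section 11.2.3).

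The cost is a few sentences of protocol text. SAP Section 10 already foresees a protocol and SAP amendment for Part 2, which could carry the change. Sample size and efficacy analyses are unaffected.
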